### **Sample Size**

From previous research, it is anticipated that the mean MSEL developmental score for children with NAID will be 90, and the standard deviation is  $\pm 15$ . To detect a 6 point difference in post-treatment MSEL developmental score between treatment and placebo group, with a power of 80% and a significance level of 5% will require a total sample size of 150 (75 per group).

With an estimated prevalence of NAID of 10%, it is anticipated that screening approximately 1500 children will identify 150 children with NAID to be randomized over a 4 year period.

Expecting potential drop-outs and withdrawals to be 0-20% a total of 180 NAID children will be randomized. For the non-randomized children (IDA and IS), it is anticipated that the mean MSEL developmental score for children with IDA will be 85 and the mean developmental score for IS children will be 100 with a standard deviation of  $\pm 15$ . From the screening cohort of 1500 it is anticipated that 1-2% will have IDA (n=25) and an equal number of randomly selected children with IS (n=25) will be sampled for comparison. To randomly select children with IS, once a child with IDA is identified the immediate next child identified with IS and agrees to participate will be enrolled in the trial.

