### **Statistical Analysis**

From the screening cohort, the baseline characteristics of the three groups (NAID, IDA, IS) will be compared with descriptive statistics and significance testing. Categorical variables will be compared with a chi-square test and that continuous variables will be compared with an ANOVA (or non-parametric equivalent). For the participants with NAID randomized to treatment or placebo groups, no significance testing will be performed on the baseline characteristics); however, we will note any imbalances that have arisen by chance which may be clinically meaningful. All children with NAID randomized to treatment or placebo will be analyzed in the group to which they were randomized following the intention to treat principle. In the primary analysis, the difference in developmental and hematologic measures in children with NAID randomized to treatment versus placebo will be assessed using linear regression (ANCOVA method) with the initial baseline measures included as the adjusting variable. In a secondary analysis, additional co-variates of clinical or statistical significance (including, parent education, family income) will be included in the model. The primary analysis will be a fixed effects model, ignoring stratification by clinic site. A secondary analysis will include a confirmatory analysis using a mixed effects model with interventions and MSEL scores as the fixed effect and clinic site as the random effects. Although efforts to ensure complete data collection and participant follow up will be maximized, analytic strategies to handle missing data will include imputation techniques, if appropriate. If >20% of participants are lost to follow-up a per protocol analysis will be carried out in addition to the intention to treat analysis.

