**Research Question in PICOT format:**

P = Pre-school children aged 18-36 months identified as having NAID (defined as serum ferritin <12 µg/L and hemoglobin >110 g/L) enrolled in the TARGet Kids! Research Network program

I = Oral iron (6mg elemental iron/kg/day in two divided doses) plus parental dietary counselling

C = Placebo plus parental dietary counseling

O = Hematological indices (serum ferritin and hemoglobin level), Growth parameters (weight and height)

T = Four (4) months

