**Sample size:**

The sample for this sub-study will be the first 40 NAID children enrolled in the randomized trial. Based on previous literature it has been shown that 1.2 cm improvement in children's height is a clinically significant improvement . Thus it has been found that a sample of 40 will have 90% power to detect a difference of 1.2 cm improvement in height (with a SD=1), at 0.05% significance level.

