**Analysis:**

An analysis of variance using multiple linear regression procedure to examine the association between the post-intervention differences in hematological and growth parameters of the two intervention groups will be carried out after adjusting for the baseline growth and serum ferritin measurements.

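### Sub-study #2 pairs 90% power for 40 children with a 0.05% significance level. At that level power is about 51%, and the level is most likely a slip for 5%.

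*Combined protocol and SAP*

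**What the plan says.** The sample for Sub-study #2 is fixed in its own sample-size paragraph: "The sample for this sub-study will be the first 40 NAID children enrolled in the randomized trial". The justification follows: 40 children are said to have "90% power to detect a difference of 1.2 cm improvement in height (with a SD=1), at 0.05% significance level". The paragraph names no test, no sidedness and no allowance for loss to follow-up. It also does not say whether the SD of 1 is that of the four-month change in height, of attained height, or of the residual after baseline adjustment.

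The main trial's Sample Size section is planned "with a power of 80% and a significance level of 5" per cent. For attrition it reads "Expecting potential drop-outs and withdrawals to be 0-20" per cent.

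The sub-study's PICOT statement lists as outcomes "Hematological indices (serum ferritin and hemoglobin level), Growth parameters (weight and height"). Its Analysis paragraph plans a multiple linear regression "after adjusting for the baseline growth and serum ferritin measurements". In the main trial, the Statistical Analysis section models the developmental and hematologic measures "with the initial baseline measures included as the adjusting variable".

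**The concern.** Read literally, 0.05% is a two-sided threshold of 0.0005, which is 100 times stricter than the main trial's 5%. The sub-study is a randomized comparison that will be unblinded and analysed separately while the trial continues, and this is the only significance level given for it. A reader therefore cannot tell which threshold will be applied to the growth and haematological results, and cannot obtain the stated power from the stated inputs. If the printed level were meant, the sub-study would have roughly an even chance of detecting its target difference. If 5% were meant, the size is adequate and only the text needs repair.

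The undefined SD matters for a different reason. The power claim rests on it, and a modestly larger SD for the quantity actually analysed would take the power below 90% even at 5%.

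**Working it through.** **Inputs.** From the sub-study's sample-size paragraph: total 40, difference 1.2 cm, SD 1, level 0.05% = 0.0005, power 90%. Equal groups of 20 are inferred from the two-arm block randomization and the equal groups of the main trial. From the main Sample Size section: level 5%, losses 0–20%. The two-sided unadjusted t-test is an assumption, because the plan names no test for this calculation.

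**Formula.** With n per group, the noncentrality is δ = 1.2 / (SD × √(2/n)), with 2n − 2 degrees of freedom. Power is the probability that a noncentral t variable exceeds the critical value. The opposite tail is negligible here.

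**Attempt to reproduce the stated 90% at 0.05%.** With n = 20 and SD = 1, δ = 1.2 / √0.1 = 3.795 on 38 degrees of freedom. The two-sided critical value at 0.0005 is 3.806. The critical value sits almost on the noncentrality, so power is close to one half: 50.6%. A simulation of 200,000 trials gave 50.4%.

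Other readings of the printed level also miss 90%:

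- Normal approximation: Φ(3.795 − 3.481) = 62.3%.
- One-sided test: 59.3% (t) or 69.3% (normal).
- Taking 40 as the number per group, which the text does not say: 95.3% (t) or 97.0% (normal).

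**Size needed for 90% at 0.05%.** By the t-test, 34 per group gives 89.2% and 35 per group gives 90.6%, so 70 children. The normal approximation gives 2 × (3.481 + 1.282)² / 1.2² = 31.5, so 32 per group, or 64 children.

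**The same calculation at 5%, SD 1.**

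| Analysed per group | Loss from 40 | Power (two-sided t) |
|---|---|---|
| 20 | 0% | 95.9% |
| 18 | 10% | 93.8% |
| 16 | 20% | 90.7% |
| 15 | 25% | 88.7% |

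The smallest size giving 90% at 5% is 16 per group, or 32 children, and 32 / (1 − 0.20) = 40. The printed 40 and 90% therefore both follow from a 5% level with the top of the main trial's loss range. The sub-study paragraph does not state that allowance, so this reconstruction is an inference.

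**Sensitivity to the SD, at 5%.** The SDs above 1 are assumptions, since the documents give only SD = 1.

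| SD of the analysed quantity | Power, 40 analysed | Power, 32 analysed |
|---|---|---|
| 1 | 96% | 91% |
| 1.25 | 84% | 75% |
| 1.5 | 69% | 59% |
| 2 | 46% | 38% |

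Power stays at 90% or more up to an SD of about 1.14 with 40 analysed and about 1.01 with 32.

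**Covariates.** Hemoglobin is a listed sub-study outcome, but the sub-study model names only baseline growth and serum ferritin as adjusters. Because allocation is randomized, omitting baseline hemoglobin does not bias the comparison. It gives up precision, by an amount that cannot be computed because the documents give no correlation between baseline and follow-up hemoglobin.

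**The case against.** The strongest reply is that this is one misplaced percent sign. The main trial's 5% makes the intention clear, 40 children exceed 90% power at 5%, and nothing about enrolment changes. That is largely right and is why the point is minor. It does not remove the need to correct the text: this is the sub-study's only stated error rate, and replacing the level alone would leave 90% printed where 40 analysed children give 96%.

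A second reply is that 51% belongs to an unadjusted t-test, whereas the plan is a baseline-adjusted regression. If SD = 1 is an unadjusted SD, multiplying it by √(1 − r²) gives about 81% power at 0.05% for a baseline correlation of 0.6 and 92% for 0.7, so a correlation near 0.68 would rescue the printed statement. The arithmetic is correct, but the documents give no correlation and the sample-size paragraph mentions none.

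A third reply is that the sentence speaks of improvement in height, so SD = 1 most naturally means the SD of change, and the larger SDs are hypothetical. That reading is plausible. The larger SDs show only why the definition should be stated; they are not evidence that the sub-study is underpowered.

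Finally, the hemoglobin covariate is a modelling point rather than arithmetic, and the main-trial wording does not literally say that each measure is adjusted for its own baseline, although that is the natural reading. The main trial also analyses hemoglobin with baseline adjustment, so any loss of precision is confined to the sub-study. It stands only as a free improvement.

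**Conclusion.** The concern holds, as a minor reporting error. The stated power cannot be obtained at the printed level: it is 51% to 62% for a two-sided comparison, depending on the formula, against the claimed 90%. The most likely explanation is that 5% was intended. In that case the claim of 90% is met, with 96% if all 40 children are analysed and 91% if 32 are, and the sub-study is not underpowered on its stated inputs.

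This rests on equal groups, a two-sided unadjusted test and SD = 1 for the analysed quantity. That 5% was meant, and that a 20% loss lies behind the 40, are inferences for the sponsor to confirm. The primary developmental analysis and all sample sizes are unaffected.

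**What to change.** In the sample-size paragraph of Sub-study #2, replace 0.05% with 5%, keep 40 children, and give the basis of the power. Suggested text: *With 20 children per group, a two-sided unadjusted t-test at the 5% level has 96% power with all 40 analysed, and 91% with 20% loss, to detect a 1.2 cm difference (SD 1).* The sponsor should confirm the level, sidedness, unadjusted test and loss allowance. The same paragraph should say whether SD = 1 refers to change in height, attained height or a baseline-adjusted residual.

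In the sub-study's Analysis paragraph, add baseline hemoglobin as a covariate when hemoglobin is the outcome.

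The cost is one corrected figure, a clarification of the power basis and the SD, and one covariate already measured at screening. No new data, no additional children and no change to the sub-study's objective are needed.

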**Analysis:**

An analysis of variance using multiple linear regression procedure to examine the association between the post-intervention differences in hematological and growth parameters of the two intervention groups will be carried out after adjusting for the baseline growth and serum ferritin measurements.

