**Investigational Agent**

Active Arm: Ferrous Sulfate Oral Solution Drops USP (brand Fer-In=Sol by Mead Johnson); Strength: 75mg Ferrous Sulfate/mL = 15mg Fe++/mL; NPN # 00762954; Commercial supply donated in kind by Mead Johnson. Blinded over-labeling will be done by the SickKids Research Support Pharmacy.

Placebo Arm: The placebo is developed by the Hospital for Sick Children Compounding Pharmacy. Contains preserved water (preserved with sodium benzoate), simple syrup NF, denatonium benzoate (for bitter/medicinal taste) and food colouring (see detailed worksheet); similar in colour and taste to active; packaged in 50mL bottles identical to active Fer-in-Sol (empty bottles donated in kind by Mead Johnson).

**Trial title: Optimizing Early Child Development in the Primary Care Practice Setting: Pragmatic Randomized Trial of Iron Treatment for Young Children with Non-anemic Iron Deficiency (OptEC)**

Both active and placebo arms will be packaged in identical bottles with blinded labels. A participant information sheet that contains information regarding the study drug will be provided to parents who agree to participate in the trial.

**Outcomes** – A complete course of iron therapy is 4 months. Changes in developmental and hematologic status may be expected within this time frame. Outcomes will be measured at two time periods: baseline and 4 months after enrollment. The primary outcome will be the developmental score using the Mullen Scales of Early Learning (MSEL). The secondary outcomes will include the behavior measure (Early Childhood Behavior Questionnaire) and two laboratory measures (hemoglobin and serum ferritin levels). The analysis metric will be the mean difference in outcome between the treatment and control groups at 4 month follow up, adjusting for the baseline measures.

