- 4) *Physical measurements* – Measurement of height, weight and waist circumference of subjects and their accompanying parent, along with child head circumference, is performed using standardized anthropometric protocols. Weight is measured using a precision digital scale ( $\pm 0.025\%$  SECA, Hamburg Germany) and standing height is measured using a stadiometer (SECA, Hamburg Germany). Body Mass Index (BMI) is calculated as weight in kilograms divided by height in meters squared and categorized as percentile categories using WHO Child Growth curves (which, unlike CDC growth curves, include percentiles for children under 2 years

**Trial title: Optimizing Early Child Development in the Primary Care Practice Setting: Pragmatic Randomized Trial of Iron Treatment for Young Children with Non-anemic Iron Deficiency (OptEC)**

of age and are able to monitor the rapid rate of growth in early infancy). Blood pressure is assessed according to the guidelines of the National High Blood Pressure Education Program.

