**Pre-study screening and Baseline Measurements**

The baseline data for this trial will be the same data collected during the TARGet Kids! visit of a child. In the TARGet Kids! Program parents/caregivers of eligible children are invited to participate by letter two weeks before their scheduled well-child visit. At the time of the physician office visit, parents will complete the written consent form, questionnaires (*TARGet Kids!* child and family characteristics questionnaire, ECBQ) and physical and laboratory measurements as described above. The overall research plan is shown in a schematic (See Appendix 3: Schematic of study plan). A Parent Letter containing a short description of the OptEC trial will be given to parents of children enrolled in the TARGet Kids! Initiative and are potential candidate for the OptEC trial. This letter will state that in case found eligible the parents will be contacted by phone to invite them to participate in the OptEC trial.

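### Sub-study #2 leaves age, sex and the time between the two measurements out of its height and weight model, so ordinary growth can cost avoidable precision

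*Combined protocol and SAP*

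**What the plan says.** **Outcome and model.** The PICOT statement of Sub-study #2 names weight and height as the growth outcomes and does not standardise them for age or sex. The Analysis paragraph compares "post-intervention differences in hematological and growth parameters of the two intervention groups" by multiple linear regression, adjusting for baseline growth and baseline serum ferritin. Age, sex and the interval between measurements are not listed.

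**Size.** "The sample for this sub-study will be the first 40 NAID children enrolled in the randomized trial". The sample size paragraph states that "a sample of 40 will have 90% power to detect a difference of 1.2 cm improvement in height", with an SD of 1 and a significance level printed as 0.05%. It does not say whether that SD refers to attained height, to gain, or to the residual after adjustment.

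**Timing.** Under Pre-study screening and Baseline Measurements, "The baseline data for this trial will be the same data collected during the TARGet Kids! visit of a child". Recruitment Strategy and Participant Timeline then place the laboratory result, a telephone call, a return visit and consent after that visit, with no limit on the gap. The Outcomes paragraph states "Outcomes will be measured at two time periods: baseline and 4 months after enrollment", whereas Participant Timeline counts the four months from the baseline visit. No visit window is given. The section on probable losses to follow-up has missed visits pursued by telephone until the trial ends.

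**Growth standards.** The physical measurements item under Outcome Measures has BMI "categorized as percentile categories using WHO Child Growth curves". The protocol does not apply these curves to height or weight.

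**The concern.** A child measured a month later than another has grown for a month longer, and growth slows across this age range. Baseline height carries part of the age effect, because older children are taller. It carries no information on how long each child was followed. Any spread in the interval therefore goes into the residual of the height model and competes with a 1.2 cm target in a sample of only 40.

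Allocation is randomised and blinded, so the spread should fall equally on both arms. What is at stake is the precision of the growth comparison and how a null height result would be read. The developmental outcome of the main trial is not affected.

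**Working it through.** **1. Inputs from the protocol.** N = 40, target 1.2 cm, SD 1 and stated power 90% (Sub-study #2, Sample size). I take 20 per arm, because the main trial plans equal groups (Sample Size).

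**2. The stated power.** For two means with n per arm, power = Φ(δ / (SD·√(2/n)) − z).
- δ / (SD·√(2/n)) = 1.2 / (1 × √0.1) = 1.2 / 0.3162 = 3.795.
- Two-sided 5%: Φ(3.795 − 1.960) = Φ(1.835) = 96.7% (95.9% by noncentral t).
- Two-sided 0.05%, as printed: Φ(3.795 − 3.481) = Φ(0.314) = 62.3% (50.6% by t).

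Neither reproduces 90%. The printed level is a separate matter; everything below uses a two-sided 5% level.

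**3. Noise from an unequal interval.** The documents give no growth rate and no spread of intervals, so both are assumed. If height grows v cm per month and the interval has SD s months, the added noise is x = v·s and the total SD is √(1 + x²). This treats the SD of 1 as excluding the noise. The two ends of 0.6 to 1.0 cm per month give:

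| Interval SD (months) | x at 0.6 (cm) | Power | x at 1.0 (cm) | Power |
|---|---|---|---|---|
| 0.5 | 0.30 | 95% | 0.50 | 92% |
| 1.0 | 0.60 | 90% | 1.00 | 77% |
| 1.5 | 0.90 | 81% | 1.50 | 56% |

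For example, at x = 1.00 the total SD is √2 = 1.414, and Φ(3.795/1.414 − 1.960) = Φ(0.723) = 77%.

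Noise equal to the 1.2 cm target needs an interval SD of 1.2/1.0 = 1.2 months to 1.2/0.6 = 2.0 months.

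**4. Simulation of the planned model.** Assumptions: age uniform on 18 to 36 months; monthly growth falling linearly from 1.0 to 0.6 cm or from 0.9 to 0.7 cm; interval of 4 months plus a skewed lag with mean 1.5 months; residual SD 1 cm; true effect 1.2 cm. Ranges cover the two growth patterns and repeated runs.

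| Interval SD (months) | Power, model adjusted for baseline only | Power, age, sex and interval added |
|---|---|---|
| 0 | 91-95% | about 92-94% |
| 0.5 | 88-91% | about 92-94% |
| 1.0 | 78-82% | about 92-94% |
| 1.5 | 62-71% | about 92-94% |

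A second calculation is milder: 91-93%, 84-86% and 75-78% at interval SDs of 0.5, 1.0 and 1.5 months. It assumed somewhat slower growth (0.75-1.0 cm per month falling to 0.5-0.75), a mean interval of 4.5 months and intervals cut off below 3 months. The direction is the same.

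**5. Which covariate matters.** With a constant interval, adding age and sex changes power by at most about 2 percentage points, because baseline height already carries most of what age would. Nearly all of the loss comes from the spread of the interval.

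**The case against.** The strongest reply is that unequal intervals are not established. If follow-up is counted from the baseline visit, as Participant Timeline has it, the planned height-to-height interval can be a constant four months. The Ethical Considerations section also has blood results reaching the physician within 24 hours, which shortens the first step between screening and enrollment. This stands in part. The protocol permits unequal intervals but does not show them: the Outcomes paragraph uses the other anchor, and neither passage sets a window.

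Second, the design has slack. At 5% the calculation gives about 96% rather than 90%. By noncentral t, added noise up to about 0.55 cm still leaves about 90%, which is an interval SD of roughly 0.55 to 0.9 month (0.55/1.0 to 0.55/0.6). This stands: with tightly timed visits there is little or no shortfall from the stated power.

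Third, the undefined SD of 1 may already contain ordinary growth variation, in which case step 3 counts it twice. That cannot be excluded. The covariates remain worthwhile either way: if the SD includes the noise they raise power, and if it does not they protect it.

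A reader might infer that ordinary growth adds noise as large as the 1.2 cm target. The documents do not support that. They give no growth rate, lag or lag spread, and under the assumed rates it takes an interval SD well above one month. Nor do they support reading this as bias between the arms, unless visit timing were to differ by arm.

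**Conclusion.** The point holds as an avoidable loss of precision in the growth comparison of Sub-study #2. The omission of age, sex and interval, the two time anchors and the absence of a window are plain in the text. The size is conditional on an assumed growth rate, an assumed interval spread, an SD of 1 that excludes this variation, and a 5% level. The loss is negligible with a constant interval and at most a few points at an interval SD of half a month. It reaches about 10 to 15 points at one month and 20 to 30 points at 1.5 months. The change is worth making because it is cheap and the sample is small, not because a serious loss has been shown.

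**What to change.** In the Analysis paragraph of Sub-study #2, add age at baseline, sex and the number of days between the two measurements as covariates in the height and weight models. Alternatively, analyse WHO height-for-age and weight-for-age z-scores computed at the exact age on each measurement date. Specify the choice before the first 40 children are unblinded for this analysis.

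The Outcomes paragraph and Participant Timeline must also be reconciled on the point from which the four months are counted. It would help to state in the sample size paragraph what the SD of 1 measures.

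**Cost.** The covariates use up to three degrees of freedom among 40 children. The planned model has 40 − 4 = 36 residual degrees of freedom (intercept, arm, baseline growth, ferritin), which would fall to 33. In simulation this costs about half a percentage point of power at most when the interval is constant. With z-scores, the 1.2 cm target has to be re-expressed. Age is already needed for eligibility, and age and sex for the WHO BMI percentiles. The documents do not list the recorded fields, so it should be confirmed that both measurement dates are captured.

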**Randomization, Stratification, Blocking and Sequence Generation**

Randomization will be stratified by clinic site. Block randomization will be generated with blocks of variable sizes. An advantage of block randomization is that group sizes are similar at the end of each block enrolled. The biostatistician will generate the randomization sequence for each clinic site using computer-generated random numbers.

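### Sub-study #2 makes hemoglobin an outcome but leaves baseline hemoglobin out of its stated covariates, so its hemoglobin estimate is less precise than the collected data allow

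*Combined protocol and SAP*

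**What the plan says.** The outcome line of Sub-study #2 (Research Question in PICOT format) reads "Hematological indices (serum ferritin and hemoglobin level), Growth parameters (weight and height"). So there are four outcomes, and hemoglobin is one of them.

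The Analysis paragraph of Sub-study #2 gives a single model statement. It concerns the "post-intervention differences in hematological and growth parameters of the two intervention groups" and says the regression "will be carried out after adjusting for the baseline growth and serum ferritin measurements". Height, weight and ferritin therefore have their own baseline among the named covariates. Hemoglobin does not, and the sub-study text gives no reason.

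The missing covariate is available. Outcome Measures lists hemoglobin among the laboratory measures for the whole screening cohort. Data Collection Methods has blood taken at the TARGet Kids! visit and again at four months.

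The main trial handles the same outcome differently. Outcomes lists hemoglobin as a secondary outcome and defines the metric as the 4-month mean difference adjusted for baseline. Statistical Analysis specifies ANCOVA for the developmental and hematologic measures "with the initial baseline measures included as the adjusting variable".

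On size, the sub-study states: "The sample for this sub-study will be the first 40 NAID children enrolled in the randomized trial". Its power statement concerns height only.

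**The concern.** In a small randomized comparison, the baseline value of an outcome is usually the most useful covariate. It removes outcome variation that has nothing to do with treatment, and it corrects for whatever baseline difference chance produced. Following the stated list would do this for three outcomes and not for the fourth.

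At stake are the width of the hemoglobin interval and its exposure to chance imbalance among 40 children. There is also a timing issue. The sub-study provides for allocation of these children to be revealed to one co-investigator for the hematological and growth outcomes. If the covariate is added only after that, the choice could be questioned as post hoc.

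**Working it through.** **Stated figure.** The documents give no power, SD or target difference for the hemoglobin comparison. The sub-study's one figure, "90% power to detect a difference of 1.2 cm improvement in height (with a SD=1), at 0.05% significance level", is for height. It does not reproduce directly: 20 per arm gives 96.7% power at two-sided 5%, and 62% at the printed 0.05%, by normal approximation. That is a separate matter and does not enter below.

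**Inputs from the documents**
- n: 40 children. Randomization is in blocks and the plan notes that "group sizes are similar at the end of each block enrolled", so take about 20 per arm.
- Hemoglobin: mean 122.1, SD 8.84 g/L (Appendix 2).
- Entry requires hemoglobin of at least 110 g/L (Eligibility for Randomization).

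**Assumptions**
- Baseline and 4-month hemoglobin are bivariate normal with SD 8.84 at both times before selection.
- The underlying correlation r is 0.3, 0.5 or 0.7. The documents give none; the internal pilot estimates one only for developmental scores.
- The growth and ferritin covariates are unrelated to hemoglobin (relaxed in step 6).

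**Step 1, baseline SD in the trial.** Cutting Normal(122.1, 8.84) at 110 gives an SD of 7.59 g/L (variance 57.57).

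**Step 2, chance baseline gap.** SD of the difference in arm means = 7.59 × √(2/20) = 2.40 g/L. A gap above 3 g/L in either direction has probability 2 × [1 − Φ(3/2.40)] = 21%. With the uncut SD of 8.84, the gap SD is 2.80 g/L and the probability 28%.

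**Step 3, how much carries over.** Without baseline hemoglobin in the model, a gap shifts the 4-month difference by slope × gap. Selecting on baseline leaves the slope at r, so the share of a 2.40 g/L gap is r × 2.40.

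**Step 4, residual variance.** The 4-month variance is 8.84²(1 − r²) + r² × 57.57. Adding baseline hemoglobin leaves 8.84²(1 − r²). The proportion removed is the squared within-trial correlation, which is r × 7.59 divided by the 4-month SD.

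| Assumed r | Carried over (g/L) | 4-month variance | Residual variance | Within-trial correlation | Variance removed | Equivalent n = 40/(1 − removed) |
|---|---|---|---|---|---|---|
| 0.3 | 0.7 | 76.3 | 71.1 | 0.26 | 7% | 43 |
| 0.5 | 1.2 | 73.0 | 58.6 | 0.44 | 20% | 50 |
| 0.7 | 1.7 | 68.1 | 39.9 | 0.64 | 41% | 68 |

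**Step 5, power illustration.** The documents name no hemoglobin target, so 6 g/L is assumed. By the noncentral t (two-sided 5%, 20 per arm, 38 degrees of freedom unadjusted and 37 adjusted), power goes from 56% to 59%, 58% to 67%, and 61% to 83% for the three values of r.

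**Step 6, does ferritin stand in for hemoglobin?** Suppose baseline ferritin correlates at q with baseline hemoglobin and relates to 4-month hemoglobin only through it. The residual variance factor is then 1 − (rq)² with ferritin alone and 1 − r² with both. At r = 0.5, ignoring the entry cut, adding hemoglobin to a model that already has ferritin multiplies the variance by 0.75/0.99 = 0.76 (q = 0.2) or 0.75/0.96 = 0.78 (q = 0.4). With no help from ferritin the factor is 0.75. On these assumed values ferritin recovers little.

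**Step 7, the change-score reading.** If the outcome were change from baseline, its variance would be the residual variance plus (1 − r)² × 57.57, or 99.3, 73.0 and 45.0. ANCOVA variance would be 71.1/99.3 = 0.72, 58.6/73.0 = 0.80 and 39.9/45.0 = 0.89 of that. A change score also over-corrects a chance gap, by (1 − r) × gap in the other direction.

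**The case against.** **Wording.** The Analysis paragraph is one loosely worded sentence and does not write out a model per outcome. It could mean growth outcomes with baseline growth and hematologic outcomes with baseline ferritin, or it could mean change scores. Both readings are possible, but neither closes the gap. The first still omits baseline hemoglobin, and the second is less precise than ANCOVA (step 7).

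**Size.** The correlation and the 6 g/L difference are assumed. Appendix 2 covers all tested children aged 12 to 36 months, not the trial population of 18 to 36 months with ferritin at or below 12 µg/L. The first ferritin quartile there is 15.55 µg/L, so eligible children are a minority tail, and cutting on hemoglobin alone does not reproduce them. This stands. The gain runs from slight to substantial, and only its direction is secure.

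**Consequence.** Sub-study #2 is a thesis sub-study sized on height. The main trial's hemoglobin analysis uses all randomized children and adjusts for baseline. This also stands and limits the importance of the point.

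**Stronger readings that the documents do not support.**
- A reader might infer that the hemoglobin comparison is biased, or that a baseline gap passes into it in full. Randomization protects against bias on average, and only the slope share of a gap carries over.
- A reader might infer that the sub-study and main-trial hemoglobin estimates cannot be compared. In a randomized linear model both target the same mean difference; they differ in precision and in the children included.
- A reader might infer that ferritin and growth should be dropped as covariates. Nothing in the documents shows that they do harm.

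**Conclusion.** The point holds as an avoidable loss of precision. Hemoglobin is the one outcome of Sub-study #2 whose own baseline is missing from the named covariates. The value is collected in every child, and the natural reading of the main trial's analysis is that it adjusts for it. Because the covariates are named, following the text as written gives a weaker hemoglobin analysis than the data permit.

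Under the stated normal model with 20 per arm, the loss is 7% to 41% of the hemoglobin residual variance for underlying correlations of 0.3 to 0.7. The existence of a loss needs only a non-zero correlation between baseline and 4-month hemoglobin beyond what the listed covariates explain. The primary outcome, the main trial's hemoglobin analysis and the other three sub-study outcomes are unaffected. It should be corrected, but no main-trial conclusion depends on it.

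**What to change.** In the Analysis paragraph of Sub-study #2, add baseline hemoglobin as a covariate in the hemoglobin model. State that each outcome (ferritin, hemoglobin, weight, height) is adjusted for at least its own baseline value, in line with Outcomes and Statistical Analysis. Baseline ferritin and growth need not be removed. The same sentence should say whether the dependent variable is the 4-month value or the change from baseline.

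Make the change before allocation of the first 40 children is revealed. It needs no new data, visits or participants and costs one degree of freedom. With an intercept, treatment, height, weight and ferritin in the model and 40 complete cases, residual degrees of freedom go from 40 − 5 = 35 to 34.
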